4.2. Exclusion Criteria

Any potential patient who meets any of the following criteria will be excluded from participating in the study. Each patient must not:

- 1. A history of malignancy (other than multiple myeloma) unless all treatment of that malignancy was completed at least 2 years before consent and the patient has no evidence of disease before the date of randomization. Exceptions are squamous and basal cell carcinomas of the skin, carcinoma in situ of the cervix or breast, or other non-invasive lesion that in the opinion of the investigator, with concurrence with the sponsor's medical monitor, is considered cured with minimal risk of recurrence within 3 years.
- 2. Must not have progressed on MM therapy at any time prior to screening.
- 3. Have had prior treatment/therapy with:
 - a. Daratumumab or any other anti-CD38 therapies,
 - b. Focal radiation therapy within 14 days prior to randomization with the exception of palliative radiotherapy for symptomatic management but not on measurable extramedullary plasmacytoma. Radiotherapy within 14 days prior to randomization on measurable extramedullary plasmacytoma is not permitted even in the setting of palliation for symptomatic management.
 - c. Plasmapheresis within 28 days of randomization.
- 4. Be exhibiting clinical signs of meningeal or central nervous system involvement due to multiple myeloma.
- 5. Have known chronic obstructive pulmonary disease (COPD) with a forced expiratory volume in 1 second (FEV1) <50% of predicted normal.

Note that FEV1 testing is required for patients with suspected COPD or asthma. Patients with FEV1 <50% of predicted normal (or for patients \geq 65 years of age, old FEV1 <50% or Diffusing capacity of the lung [DLCO] <50%) on screening assessment must be excluded.

- 6. Have known moderate or severe persistent asthma within the past 2 years (see Section 9.2.4), or current uncontrolled asthma of any classification. Note that patients who currently have controlled intermittent asthma or controlled mild persistent asthma are allowed in the study, provided that FEV1 is ≥50% of predicted normal.
- 7. Have any of the following:
 - a. Known history of seropositivity for human immunodeficiency virus (HIV).
 - b. Seropositive for hepatitis B (defined by a positive test for hepatitis B surface antigen [HBsAg]). Patients with resolved infection (ie, patients who are HBsAg negative but positive for antibodies to hepatitis B core antigen [anti-HBc] and/or antibodies to hepatitis B surface antigen [anti-HBs]) must be screened using real-time PCR measurement of hepatitis B virus (HBV) DNA levels. Those who are PCR positive will be excluded. EXCEPTION: Patients with serologic findings suggestive of HBV vaccination (anti-HBs positivity as the only serologic marker) AND a known history of prior HBV vaccination, do not need to be tested for HBV DNA by PCR.
 - c. Seropositive for hepatitis C (anti- hepatitis C virus [HCV] antibody positive or HCV-RNA quantitation positive), except in the setting of a sustained virologic response, defined as aviremia at least 12 weeks after completion of antiviral therapy).

Note, patients who completed treatment for hepatitis C at least 6 months prior to screening and have no detectable circulating HCV during screening may participate in the study. Such patients will be required to undergo regular assessments for HCV reactivation during the study and are to be withdrawn from the study if he/she test positive at any time during the study.

- 8. Have a concurrent medical or psychiatric condition or disease (eg, active systemic infection, uncontrolled diabetes, acute diffuse infiltrative pulmonary disease, Waldenström's macroglobulinemia, POEMS syndrome [polyneuropathy, organomegaly, endocrinopathy, monoclonal protein, and/or skin changes], or light chain amyloidosis) that is likely to interfere with the study procedures or results, or that in the opinion of the investigator, would constitute a hazard for participating in this study and/or current or history of CNS involvement by the disease under investigation.
- 9. Have any of the following:
 - a. Myocardial infarction within 6 months of randomization, or an unstable or uncontrolled disease/condition related to or affecting cardiac function (eg, unstable angina, congestive heart failure, New York Heart Association Class III-IV),
 - b. Uncontrolled cardiac arrhythmia
- 10. Have known allergies, hypersensitivity, or intolerance to boron or mannitol, sorbitol, corticosteroids, monoclonal antibodies or human proteins, or their excipients (refer to the IB) or known sensitivity to lenalidomide.

- 11. Be known or suspected of not being able to comply with the study protocol (eg, because of alcoholism, drug dependency, or psychological disorder).
- 12. Have any condition for which, in the opinion of the investigator, participation would not be in the best interest of the patient (eg, compromise the well-being) or that could prevent, limit, or confound the protocol-specified assessments. Patient is taking any prohibited concomitant therapy per Section 8.3.
- 13. Be pregnant, or breast-feeding, or planning to become pregnant or breast-feed while enrolled in this study or within 3 months after the last dose of study treatment(s). Or, if male, planning to father a child while enrolled in this study or within 3 months after the last dose of study treatment(s).
- 14. Have had major surgery within 2 weeks before randomization or will not have fully recovered from surgery, or has surgery planned during the time the patient is expected to participate in the study or within 2 weeks after the last dose of study treatment. Note, patients with planned surgical procedures to be conducted under local anesthesia may participate. Kyphoplasty or vertebroplasty are not considered major surgery.
- 15. Have received an investigational drug (including investigational vaccines) or used an invasive investigational medical device within 4 weeks or 5 pharmacokinetic half-lives, whichever is longer, before randomization or is currently enrolled in an interventional investigational study.
- 16. Have contraindications to the use of lenalidomide or daratumumab, per local prescribing information.
- 17. Have gastrointestinal disease that may significantly alter the absorption of oral drugs.
- 18. Have received vaccination with live attenuated vaccines within 4 weeks of first study agent administration
- 19. Be unable or unwilling to undergo antithrombotic prophylactic treatment.

NOTE: Investigators should ensure that all study enrollment criteria have been met during screening. If a patient's clinical status changes (including any available laboratory results or receipt of additional medical records) after screening but before the first dose of study treatment is given, such that he or she no longer meets all eligibility criteria, then the patient should be excluded from participation in the study. Section 17.4, Source Documentation, describes the required documentation to support meeting the enrollment criteria.

4.3. Prohibitions and Restrictions

Potential patients must be willing and able to adhere to the following prohibitions and restrictions during the course of the study to be eligible for participation. For restrictions related to concomitant medications, please refer to Section 8.

1. A woman of childbearing potential must remain on a highly effective method of birth control (see inclusion criteria). Contraception must begin 4 weeks before initiating treatment with daratumumab and continue during the Treatment Phase, during dose interruptions and continuing for 4 weeks after the last dose of lenalidomide and 3 months following of the last dose of daratumumab.

Reliable contraception is indicated even where there has been a history of infertility, unless due to hysterectomy. In addition, women must not donate ova during the study, for 4 weeks after the last dose of lenalidomide, and for 3 months after the last dose of daratumumab.

- 2. A man who has not had a vasectomy and who is sexually active with a woman of childbearing potential must agree to use a barrier method of birth control (eg, condom with spermicidal foam/gel/film/cream/suppository), and all men must not donate sperm during the study, for 4 weeks after the last dose of lenalidomide, and for 3 months after the last dose of daratumumab. The exception to this restriction is that if the patient's female partner is surgically sterile, a second method of birth control is not required.
- 3. All patients must adhere to the local lenalidomide Risk Evaluation and Mitigation Strategy (REMS) program (when lenalidomide is supplied locally), or the lenalidomide Global Pregnancy Prevention Plan (when lenalidomide is supplied centrally and no local lenalidomide REMS program exists) in Attachment 3.
- 4. During the Treatment Phase, pregnancy test requirements during the study are shown in the Time and Event Schedule Part 1. Additional pregnancy tests may be required, as specified in the local lenalidomide REMS (where lenalidomide is supplied locally) or the lenalidomide Global Pregnancy Prevention Plan (where lenalidomide is supplied centrally, and no local lenalidomide REMS program exists).
- 5. Typically, IV contrast is not used in CT scanning of patients with secretory multiple myeloma because of the risk to the kidney. If administration of IV contrast is necessary, then adequate precautions including hydration are indicated.
- 6. Patients must not donate blood during therapy and for at least 4 weeks following discontinuation of lenalidomide.

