 - a. Must not be of childbearing potential: defined as premenarchal; postmenopausal (>45 years of age with amenorrhea for at least 12 months or any age with amenorrhea for at least 6 months and a serum follicle stimulating hormone level >40 IU/L); permanently sterilized (eg, bilateral tubal occlusion [which includes tubal ligation procedures as consistent with local regulations], hysterectomy, bilateral salpingectomy, bilateral oophorectomy); or otherwise be incapable of pregnancy.

or

- b. If of childbearing potential:
 - i. Must commit to either abstain continuously from heterosexual sexual intercourse or to use 2 methods of reliable birth control simultaneously during the treatment period.

Sexual abstinence is considered a highly effective method only if defined as refraining from heterosexual intercourse during the entire period of risk associated with the study drug.

Methods of reliable birth control include 1 highly effective form of contraception (tubal ligation, intrauterine device, hormonal [birth control pills, injections, hormonal patches, vaginal rings, or implants], or partner's vasectomy) and 1 additional effective contraceptive method (male latex or synthetic condom, diaphragm, or cervical cap).

Contraception must begin 4 weeks prior to dosing.

Reliable contraception is indicated even where there has been a history of infertility, unless due to hysterectomy or bilateral oophorectomy.

and

ii. Must have 2 negative serum or urine pregnancy tests during screening, first within 10 to 14 days prior to dosing and the second within 24 hours prior to dosing.

and

iii. Must agree not to donate eggs (ova, oocytes) for the purposes of assisted reproduction during the study and for 4 weeks after the last dose of lenalidomide and for 3 months after the last dose of daratumumab

- 8. If a man who is sexually active with a female of childbearing potential:
 - a. Must agree to use a latex or synthetic condom, even if he had a successful vasectomy. and
 - b. Must agree to not donate sperm during the study and for 4 weeks after the last dose of lenalidomide and for 3 months after the last dose of daratumumab.
- 9. Must sign (or have his/her legally acceptable representative sign) an informed consent form (ICF) indicating that he or she understands the purpose of and procedures required for the study and is willing to participate in the study.
- 10. Is able, and agrees, to the prohibitions and restrictions specified in this protocol.

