Further information about the REMS programs is available at: www.celgeneriskmanagement.com

1.	For women of childbearing potential, adequate contraception, without interruption, must
	begin 28 days before starting lenalidomide and continue during the Treatment Phase,
	during any dose interruptions, and for at least 4 weeks after the last dose of lenalidomide.
	All women must not donate ova during the study and for at least 4 weeks after the last
	dose of lenalidomide. All women must not breastfeed while taking lenalidomide and for
	at least 28 days after the last dose of lenalidomide.
2	Prior to starting lenalidomide, two negative pregnancy tests are required. The first
	pregnancy test must be performed within 10 to 14 days prior to the start of lenalidomide

	and the second pregnancy test must be performed within 24 hours prior to the start of lenalidomide.
3	During the Treatment Phase, pregnancy tests are required weekly during Cycle 1 and then monthly in subsequent cycles in women with regular menstrual cycles or every 2 weeks in women with irregular menstrual cycles. A pregnancy test is also required at the End of Treatment Visit and 28 days following the last dose of lenalidomide for women with regular menstrual cycles or 14 and 28 days following the last dose of lenalidomide for women with irregular menstrual cycles. Additional pregnancy tests may be required, as specified in the local lenalidomide REMS (where lenalidomide is supplied locally) or the Lenalidomide Global Pregnancy Prevention Plan in Attachment 3 (where lenalidomide is supplied centrally and no local lenalidomide REMS program exists).
4	A man who is sexually active with a pregnant woman or a woman of childbearing potential must always use a latex or synthetic condom during the study and for at least 4 weeks after discontinuing lenalidomide (even if he has undergone a successful vasectomy). All men must not donate semen or sperm during the study, during dose interruptions, or for at least 4 weeks after the last dose of lenalidomide.
5	Because of the embryo-fetal risk of lenalidomide, all patients must adhere to the local lenalidomide REMS program (when lenalidomide is supplied locally), or the lenalidomide Global Pregnancy Prevention Plan provided in Attachment 3 (when lenalidomide is supplied centrally and no local lenalidomide REMS program exists).

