For a female NOT of childbearing potential, lenalidomide is contraindicated unless all of the following are met (i.e., all females NOT of childbearing potential must be counseled concerning the following risks and requirements prior to the start of lenalidomide study therapy):

• She acknowledges that she understands the hazards and necessary precautions associated with the use of lenalidomide

Traces of lenalidomide have been found in semen. Male patients taking lenalidomide must meet the following conditions (ie, all males must be counseled concerning the following risks and requirements prior to the start of lenalidomide study therapy):

- Understand the potential teratogenic risk if engaged in sexual activity with a pregnant female or a female of childbearing potential
- Understand the need for the use of a condom even if he has had a vasectomy, if engaged in sexual activity with a pregnant female or a female of childbearing potential.

Contraception

Females of childbearing potential (FCBP) enrolled in this protocol must agree to use two reliable forms of contraception simultaneously or to practice complete abstinence from heterosexual contact during the following time periods related to this study: 1) for at least 28 days before starting study drug; 2) while participating in the study; 3) dose interruptions; and 4) for at least 28 days after study treatment discontinuation.

The two methods of reliable contraception must include one highly effective method and one additional effective (barrier) method. FCBP must be referred to a qualified provider of contraceptive methods if needed. The following are examples of highly effective and additional effective methods of contraception:

- Highly effective methods:
 - Intrauterine device (IUD)
 - Hormonal (birth control pills, injections, implants)
 - Tubal ligation
 - Partner's vasectomy
- Additional effective methods:
 - Male condom
 - Diaphragm
 - Cervical Cap

Because of the increased risk of venous thromboembolism in patients with multiple myeloma taking lenalidomide and dexamethasone, combined oral contraceptive pills are not recommended. If a patient is currently using combined oral contraception, the patient should switch to one of the effective methods listed above. The risk of venous thromboembolism continues for 4 to 6 weeks after discontinuing combined oral contraception. The efficacy of contraceptive steroids may be reduced during co-treatment with dexamethasone.

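### Section 4.3 item 2 states a narrower male barrier rule than Section 4.1 and Attachment 3: it leaves out vasectomised men and pregnant partners and names a condom only as an example

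*Protocol*

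**What the plan says.** Protocol Section 4.3 (Prohibitions and Restrictions) opens with "Potential patients must be willing and able to adhere to the following prohibitions and restrictions during the course of the study to be eligible". The last numbered inclusion criterion in Section 4.1 ties each patient to that list: "Is able, and agrees, to the prohibitions and restrictions specified in this protocol".

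Item 2 of the list is the male rule. It begins "A man who has not had a vasectomy and who is sexually active with a woman of childbearing potential must agree" and says that such a man "must agree to use a barrier method of birth control (eg, condom with spermicidal foam/gel/film/cream/suppository". It then bars sperm donation by all men, gives periods of 4 weeks after the last lenalidomide dose and 3 months after the last daratumumab dose, and closes with an exception: no second method is needed if the partner is surgically sterile.

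The male contraception criterion in Section 4.1 reads differently: "Must agree to use a latex or synthetic condom, even if he had a successful vasectomy". Item 4 of the lenalidomide table in Attachment 3 says "A man who is sexually active with a pregnant woman or a woman of childbearing potential must always use a latex or synthetic condom", and adds that this holds after a successful vasectomy. The male counselling text in Section 1.1.1.2 of Attachment 3 has "Understand the need for the use of a condom even if he has had a vasectomy".

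**The concern.** Attachment 3 introduces the male counselling conditions by stating that traces of lenalidomide have been found in semen, and says that a teratogenic effect in humans cannot be excluded. The hazard is therefore drug in semen as well as conception. A vasectomy does not remove that hazard, so it is the wrong dividing line for a barrier rule. For the same reason a pregnant partner matters, and item 2 does not mention her.

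Section 4.3 applies both at entry and on study, so it is a natural reference for site staff. The Section 4.1 criterion is an agreement made at entry and gives no duration for condom use. A coordinator who consults item 2 alone would not ask a vasectomised man for a condom, and could treat the condom as optional among barriers for other men. What is at stake is avoidable fetal exposure.

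**Working it through.** No arithmetic applies. The check sets the current provisions side by side.

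| Place in protocol | Men covered | Partner | Method |
|---|---|---|---|
| Section 4.3 item 2 | Only those without a vasectomy | Childbearing potential | A barrier; condom with spermicide as an example |
| Section 4.1, male contraception criterion | Vasectomised men expressly included | Childbearing potential | Latex or synthetic condom |
| Attachment 3, lenalidomide table item 4 | Vasectomised men expressly included | Pregnant or childbearing potential | Latex or synthetic condom |
| Attachment 3, 1.1.1.2, male counselling | Vasectomised men expressly included | Pregnant or childbearing potential | Condom |
| Attachment 3, 1.1.1.2, male rules before starting drug | Vasectomised men expressly included | Pregnant or childbearing potential | Abstinence or condom |
| Attachment 3, 1.1.1.3, counselling form | Vasectomised men expressly included | Pregnant or childbearing potential | Abstinence or condom |

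1. **Men covered.** All five other places include vasectomised men. Only item 2 leaves them out.
2. **Partner.** Four of the five other places cover pregnant partners. The Section 4.1 criterion, like item 2, does not.
3. **Method.** Two of the five specify latex or synthetic material and three say only condom. None of the five offers another barrier.
4. **Can a man satisfy every provision at once?** Yes, by following the strictest. Section 4.1 requires every inclusion criterion to be met. Attachment 3 opens by sending participants to the Section 4.1 measures. Section 4.3 item 3, directly below item 2, binds all patients to the local lenalidomide risk-management programme or, where none exists and supply is central, to the plan in Attachment 3.
5. **How far do the backstops reach?** Male counselling at least every 28 days belongs to the Global Pregnancy Prevention Plan. Attachment 3 applies that plan where lenalidomide is supplied centrally and there is no local programme, although its Section 1.1.1.1 says it applies to all patients on lenalidomide. The content of the local programme is not in the documents, so the 28-day counselling should not be assumed at every site.
6. **Time periods.** Item 2's 3 months after daratumumab can be read as covering barrier use as well as sperm donation, and Attachment 3 item 4 gives only the 4-week lenalidomide period. Exclusion criterion 13 also uses 3 months for fathering a child. A correction that simply imported the Attachment 3 wording could shorten the period, so item 2's periods should stay.

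**The case against.** The strongest reply is that nothing here truly conflicts. Item 2 grants no permission. It is a weaker requirement sitting beneath a stricter one, and a man who obeys item 2 but not Section 4.1 is out of compliance. That stands. A reader might infer that the protocol exempts vasectomised men from condom use, but step 4 shows that it does not.

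A second reply is that the method difference is thin. The condom is the only barrier the protocol names for the man himself; the diaphragm and cervical cap appear in the lists of additional methods for female patients. This also largely stands. The example wording is loose drafting, and the documents do not show that sites are meant to accept some other barrier. The vasectomy limit and the missing pregnant partner carry the point.

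A third reply is that the affected group is small. Both arms receive lenalidomide, so a reader might attach the point to all 214 planned patients. The documents do not support that. The group item 2 leaves out is vasectomised men with a partner of childbearing potential, together with men whose partner is pregnant, and no count is given for either.

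None of these replies explains why the narrower wording should remain. Item 2 is operative text, and a fetal-exposure rule should not depend on the reader finding the stricter version elsewhere.

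**Conclusion.** The point holds as a minor safety-text correction. Item 2 has the wrong scope as to men and partners, and loose wording as to method, compared with the rest of the protocol. The stricter rule remains in force through Section 4.1, Section 4.3 item 3 and Attachment 3, so the practical risk is small. It arises only where a site relies on item 2 alone, and how often that happens cannot be judged from the documents. There is no effect on sample size, analysis or any estimate. The conclusion rests on the current protocol text, not on the amendment history.

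**What to change.** In Section 4.3 item 2:

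- Delete the qualifier that confines the rule to men without a vasectomy.
- Require a latex or synthetic condom, including after a successful vasectomy, with any partner who is pregnant or of childbearing potential.
- Keep the time periods and the sperm-donation rule as they are.
- Deal with the closing exception. If spermicide is dropped, the waiver of a second method refers to nothing. Either keep spermicide as the second method, or reword the exception to say that it waives only the second method and never the condom.
- Add a cross-reference to item 4 of the Attachment 3 lenalidomide table and to the male contraception criterion in Section 4.1. Identify that criterion by description, not by number. The available text prints number 1 twice in Section 4.1, and the Time and Events Schedule calls the archived-marrow criterion #4 where Section 4.1 shows 3. The male criterion shown as 8 is therefore probably 9 in the source.

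In Section 4.1, add pregnant partners to the male contraception criterion, so that it matches both Attachment 3 and the corrected item 2.

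The cost is a reworded item 2, a few words in Section 4.1 and a cross-reference. They can be carried in the next formal amendment with IRB approval under Section 17.1. No new procedure, data collection or analysis is needed.
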